9.7 Data Analyses

The Primary Mechanistic Outcome Measure for this study is increased functional connectivity between the L-DLPFC and dACC. The Relevant Clinical Outcome Measure is change in hypnotic analgesia as measured by change in pain thresholds. For secondary aims, the emphasis is on identifying the magnitude of effects (clinical significance, effect size) instead of statistical significance. We will test whether the change in connectivity from baseline to post-treatment is greater in the active rTMS group as compared to the sham group. Following the convention in imaging studies, we will conduct our primary analyses treating the contrast (baseline versus post) as one univariate outcome. We do not expect much variation across our narrowly defined subjects, although some variation is still possible. Given that, we will also analyze the data in the linear mixed effects modeling framework (165, 166) allowing for random intercepts (although this is not customary in imaging studies) as a way of sensitivity analysis. The same analytical strategy will be used to test the effect of rTMS on the DLPFC and dACC activity, which is Secondary

Hypothesis A (previously activity portion of Hypothesis 1a-in grant), activity during conflict task (Secondary Hypothesis C), and during post-hypnotic instruction conflict task (Secondary Hypothesis D).

We are using thermal pain stimuli percept-matched to the individual receiving the intervention. Examining the treatment-effect moderating the role of the pain level is not a primary aim of this project.

Moderator/mediator investigation: We will explore various baseline variables as potential moderators of rTMS effect. For this investigation, we will employ the McArthur approach (167, 168) for moderator analysis. We will also examine potential mediators of rTMS effect using the McArthur approach (167, 168) as well as contemporary causal mediation approaches (169-174), which we believe will provide valuable insights regarding the neuromodulation mechanism for the next phase of investigation.

Handling of missing data: We use the same sample twice to achieve enough statistical power with our moderate sample size, not to model the change between scanning sessions. With no longitudinal components, the two groups (rTMS versus sham) will be cross-sectionally compared in our primary aims. The impact of missing data due to attrition is minimal. Further, time between assessments is so narrow that the probability of having cases with missing data (dropout, attrition) is very low. As a way of assessing the impact of missing scan sessions, we will repeat our main analyses treating outcomes measured in the hypnosis scan and in the hypnotic analgesia scan as multivariate outcomes. This will allow us to include all participants in the analysis as long as one of the two scans is available. In this analysis framework, missing data will be handled assuming that it is missing at random conditional on observed scan session data (maximum likelihood estimation). Analyzing the data using both univariate and multivariate analysis approaches will also serve as sensitivity analyses. Additionally, we will include the order of scan sessions in the model to account for the carryover and order effects.

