9.7	Data Analyses.....	73
10.	DATA COLLECTION AND QUALITY ASSURANCE	76
10.1	Data Collection Forms	76
10.2	Data Management.....	76
10.3	Quality Assurance.....	78
10.3.1	Training	78
10.3.2	Quality Control Committee	78
10.3.3	Metrics.....	78
10.3.4	Protocol Deviations.....	79
10.3.5	Monitoring.....	80
11.	PARTICIPANT RIGHTS AND CONFIDENTIALITY	82
11.1	Institutional Review Board (IRB) Review.....	82
11.2	Informed Consent Forms	82
11.3	Participant Confidentiality	82

11.4 Study Discontinuation.....	83
12. COMMITTEES.....	84
13. PUBLICATION OF RESEARCH FINDINGS	85
14. REFERENCES.....	78
15. SUPPLEMENTAL MATERIAL.....	89
I. Stanford IRB-Approved Informed Consent Form	
II. TMS Stimulation Manual	
III. TMS Blinding Manual	
IV. Hypnosis and Hypnotic Analgesia Manual	

STUDY TEAM ROSTER

[name]., Principal Investigator

[REDACTED]
[REDACTED]
Stanford, CA 94305
[contact]
Fax: [REDACTED]
Email: [contact]

[name]., Principal Investigator

[REDACTED]
[REDACTED]
Stanford, CA 94305
[contact]
Fax: [REDACTED]
Email: [contact]

[name]., Co-Investigator

[REDACTED]
[REDACTED]
Palo Alto, CA 94305
Phone: [REDACTED]
Fax: N/A
Email: [REDACTED]

[name]., Co-Investigator

[REDACTED]
Stanford, CA 94305 [REDACTED]
Phone: [REDACTED]
Fax: [REDACTED]
Email: [REDACTED]

[name]., Co-Investigator

[REDACTED]
[REDACTED]
Stanford, CA 94305 [REDACTED]
Phone: [REDACTED]
Fax: [REDACTED]
Email: [REDACTED]

PARTICIPATING STUDY SITES

[name]. Principal Investigator

Stanford University
Department of Psychiatry

██████████

██████████

Stanford, CA 94305

[contact]

Fax: ██████████

Email: [contact]

[name]. Principal Investigator

Stanford University
Department of Psychiatry

██████████

Stanford, CA 94305

[contact]

Fax: ██████████

Email: [contact]

PRÉCIS

Title

Use of Repetitive Transcranial Magnetic Stimulation (rTMS) to Augment Hypnotic Analgesia

Objectives

Primary Mechanistic Objective: To determine the effect of active, inhibitory rTMS (continuous theta-burst stimulation-cTBS) over left dorsolateral prefrontal cortex (L-DLPFC) on modulating the neural network that underlies hypnotizability and hypnosis.

Relevant Clinical Objective: To determine the effect of active, inhibitory rTMS (cTBS) over L-DLPFC on enhancing hypnotic analgesia (HA) as measured by change in pain thresholds.

Secondary Objective A: *To determine the effect of active, inhibitory rTMS (cTBS) over L-DLPFC on modulating the neural network that underlies hypnotic intensity.*

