All participants will undergo the ***Hypnotic Stroop Scan Session Day***. All participants will receive the identical pre-rTMS scan session. One-half (n=50) will receive active rTMS and one-half (n=50) will receive sham rTMS (two arm, double-blind, sham-controlled). All participants will receive the identical post-rTMS scan session. Changes in resting state *functional connectivity* between L-DLPFC and dACC in the active rTMS versus the sham rTMS conditions will be assessed. This primary endpoint is a between-group comparison. We will also measure the difference in brain *activation* during the hypnotic induction, and Stroop task (after post-hypnotic suggestion) between the active and sham rTMS. This will also be a between-groups comparison. Using the *Hypnotic Induction Profile (HIP)* and *Hypnotic Intensity Scale (HIS)*, we will compare the change in hypnotizability and hypnotic intensity score between the active and sham rTMS groups.

All participants will undergo the ***Hypnotic Analgesia Scan Session Day***. All participants will complete identical pre- and post- rTMS scan session. One-half will receive active rTMS and one-half will receive sham rTMS. Changes in resting state *functional connectivity* between L-DLPFC and dACC in the active rTMS versus the sham rTMS conditions will be assessed. This primary endpoint is a between-group comparison. This scan-session also addresses a secondary aim of determining the difference in functional connectivity within the hypnotic analgesia network between the active and the sham rTMS groups. This will be a between-groups comparison. We will also compare the activation within the hypnotic analgesia network between the active and sham rTMS groups. This will be a between-groups comparison. We will also utilize a perturbation technique to probe the hypnotic induction in an alternative way. Finally, we will compare the difference in pain thresholds between the active and sham rTMS groups.

Interventions and Duration

Intervention: We will compare active versus sham rTMS as a technique for modulating the neural

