1. STUDY OBJECTIVES

1.1 Primary Mechanistic and Relevant Clinical Objectives

Primary Mechanistic Objective: To determine the effect of active, inhibitory rTMS (continuous theta-burst stimulation-cTBS) over left dorsolateral prefrontal cortex (L-DLPFC) on modulating the neural network that underlies hypnotizability and hypnosis. **In other words, the Primary Outcome Measure** is the change in functional connectivity between the L-DLPFC and the dACC in active versus sham rTMS and the effect of rTMS inhibition of activity in the DLPFC on activity in the dACC.

Primary Mechanistic Hypothesis: Active, inhibitory rTMS (cTBS) over L-DLPFC will modulate the neural network that underlies hypnotizability by producing greater increases in functional connectivity between L-DLPFC and dACC as compared to sham rTMS (sham cTBS). We hypothesize that active, inhibitory rTMS (continuous theta-burst stimulation) will produce increases in functional connectivity between the L-DLPFC and the dACC, producing a transient phenotype appearing on neuroimaging like a high hypnotizable. This increase in functional connectivity, coupled with inhibition of *activity* in the DLPFC, would be hypothesized to reduce activity in the dACC as well, which is what we have shown to be associated with entry into the hypnotic state. Thus rTMS-induced increase in functional connectivity should increase hypnotizability and, coupled with inhibited activity, enhance hypnotic intensity as well.

Relevant Clinical Objective: To determine the effect of active, inhibitory rTMS (cTBS) over L-DLPFC on enhancing the efficacy of hypnotic analgesia (HA) as measured by change in pain thresholds.

Relevant Clinical Hypothesis: Active, inhibitory rTMS (cTBS) over L-DLPFC will enhance the efficacy of hypnotic analgesia (HA) as compared to sham rTMS (sham cTBS).

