Modulation of Pain in Fibromyalgia with rTMS at dACC and DLPFC: Several groups have investigated the analgesic effect rTMS in FMS related pain (11). In a recent study, sixteen FMS patients received 20 rTMS sessions over a 4-week period. The primary outcome measure was the Brief Pain Inventory (BPI) item 5 rating ("average pain rating in the last 24 hours" expressed on a 11-point numeric rating scale with "0" being "no pain" and "10" being "worst pain imaginable") measured 4 weeks after the last modulation session. It was demonstrated that there was up to an 84% decrease in pain ratings (average decrease 31%) after active TMS when stimulating at 10 Hz compared to a control group which was stimulated with 1 Hz. L-DLPFC rTMS can be utilized in the modulation of fibromyalgia(78) with improvements in measures of pain (66). In these studies, the stimulation parameters were 10 Hz with a pulse train duration (on time) 5 seconds, power (intensity) level 120% of resting motor threshold, and an inter-train interval (off time) 10 seconds (15 second cycle time). The primary outcome measure for this study was also the Brief Pain Inventory (BPI) item 5 rating. Excitatory L-DLPFC rTMS was shown to demonstrate a mean 29% (statistically significant) reduction in pain symptoms in comparison to the FMS patient's baseline pain. Sham rTMS participants had a 4% non-significant change in daily pain from their baseline pain(66). Inhibitory rTMS over the dACC was demonstrated to not exert a clinically meaningful effect on pain, suggesting that outside of hypnosis, inhibitory rTMS alone should not exert an independent effect on pain(11).

Intervention Regimen: We will employ a spaced continuous theta-burst technique that is capable of providing a change in neural activity, which will last for the entirety of each of the participant's

post-rTMS scanner sessions(27-30, 79).

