6. STUDY PROCEDURES

6.1 Schedule of Evaluations

Assessment	Redcap Screening: Online	Baseline, Enrollment, Randomization: Visit 1 (Day 0)	TMS Target Scan Day	Hypnotic Stroop Scan Day	Hypnotic Analgesia Scan Day
Online Consent	X				
Informed Consent Form 1 (Screening)		X			
Demographics	X				
Screening Forms	X	X	X	X	X
Medical History	X	X			
Current Medications	X	X		X	X
Informed Consent 2 (Full)		X			
Blood Chemistries		X			
Urine Analysis				X	X
Inclusion/Exclusion Criteria	X	X			
Enrollment/Randomization		X			
Stimulation Log				X	X
Concomitant Medications		X		X	X
Adverse Events		X	X	X	X
HIP/SOARS		X		X	X
HIS				X	X
Pain Induction					X
Stroop Task				X	

Table 2: The table includes the schedule for all of the assessments.

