Pre-rTMS Analgesia Session: This hour-long scan session includes all of the pre-rTMS questionnaires, behavioral evaluations, and scans necessary to compare to the post-rTMS.

- Medication Washout, Drug Screen, Pregnancy Test Form: This form will be administered at the beginning of each pre-rTMS assessment to ensure medication washout compliancy (if applicable), document drug screen results, and screen for pregnancy (if applicable).
- Pain Thresholds: Baseline heat-pain thresholds and supra-pain thresholds will be determined for each volunteer based on responses to computer-controlled thermal stimuli delivered to the left forearm with a 30 x 30 mm advanced thermal stimulator (ATS) thermode (Medoc Pathway Model ATS). Thresholds will be measured using a standard method of limits protocol. Specifically, thermal pain threshold and tolerance values will be assessed outside the MRI scanner to identify a moderate pain intensity value that will be applied during the hypnotic and non-hypnotic analgesia MRI scans. The moderate pain intensity value will be used for both pre- and post-rTMS analgesia MRI sessions.
- Hypnotic Induction Profile: This administration of the HIP will serve as the baseline measure for comparison after the rTMS stimulation session(87). HIP will be measured on three separate occasions throughout the stroop assessment visit - 1) immediately following the pre-rTMS analgesia MRI session, 2) immediately following rTMS, and, 3) immediately following the post-rTMS analgesia MRI session.
- Pre-TMS Scans
 - Structural Acquisition (T1): This structural scan is necessary for several reasons: demonstration that the participant's brain is structurally normal, imaging analysis, and rTMS targeting (81).
 - BOLD fMRI Acquisitions
 - Resting State: This is the baseline scan required for the primary endpoint. Individuals with higher hypnotizability have been demonstrated to have

higher functional connectivity between the dorsolateral prefrontal cortex and the dorsal anterior cingulate cortex (31).

- Pain Induction: Functional brain responses to acute, thermally, induced pain, will be measured using the moderate pain intensity value following hypnosis (Hypnotic Analgesia) and non-hypnosis (Non-Hypnotic Analgesia) audio instructions. These acquisitions will be randomized to prevent order effects. Hypnotic analgesia during pain induction has been demonstrated to be instruction specific (38, 44) and produce alterations in functional connectivity (123).

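### The clinical outcome is change in pain thresholds, but Section 6 lists a threshold test only before rTMS, while Section 9.6.1 describes a post-rTMS temperature series and a separate ratings ANOVA; these are not reconciled

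*Combined protocol and SAP*

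**What the plan says.** The outcome variable is named the same way throughout. The Précis gives the clinical objective as the effect of stimulation "on enhancing hypnotic analgesia (HA) as measured by change in pain thresholds" and ends its overview with "Finally, we will compare the difference in pain thresholds between the active and sham rTMS groups". Section 1.1 repeats it ("on enhancing the efficacy of hypnotic analgesia (HA) as measured by change in pain thresholds"), and so does Section 9.7: "The Relevant Clinical Outcome Measure is change in hypnotic analgesia as measured by change in pain thresholds".

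The procedures are in Section 6. Before rTMS, Section 6.2.2 says that "thermal pain threshold and tolerance values will be assessed outside the MRI scanner to identify a moderate pain intensity value", and then: "The moderate pain intensity value will be used for both pre- and post-rTMS analgesia MRI sessions". After rTMS, the analgesia session in Section 6.2.5 is introduced as containing all the behavioural evaluations needed for comparison with the pre-rTMS session. Its list is the HIP, a T1 scan, resting state and pain induction at the same moderate stimulus, with hypnosis and non-hypnosis runs. It has no threshold item. The schedule in Section 6.1 has one relevant row, "Pain Induction", on the analgesia day.

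The analyses are in Section 9. For the Relevant Clinical Outcome, Section 9.6.1 compares changes in mean pain ratings by ANOVA at the 0.05 level. For the Relevant Clinical Hypothesis, it describes temperatures for threshold and moderate pain before rTMS + HA and at 5-minute intervals for 30 minutes afterwards, tested by linear mixed modelling at 0.05. The separate SAP describes tests of HIP scores and of the blind only.

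**The concern.** A change needs a value before and a value after. Someone following Section 6 as written would collect the first and not the second, and the defined outcome could not be computed. Someone following Section 9.6.1 would collect a series for which Section 6 gives no slot, and would then have no stated rule for turning it into one treatment effect. A threshold temperature and a rating at a fixed temperature are different variables. With each tested at 0.05 and neither test ranked, either could be presented as the clinical result once the data are seen.

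A smaller, interpretive point sits beside this. The hypothesis is that rTMS enhances HA. Every pain test in Section 9 that identifies its condition uses rTMS + HA. The protocol also acquires a post-rTMS non-hypnosis pain run, but no stated test is described as using it.

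**Working it through.** **1. Outcome, procedure and analysis side by side**

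| Element | Where | What it gives |
|---|---|---|
| Outcome variable | Précis, 1.1, 9.7 | Change in pain threshold |
| Pre-rTMS threshold | 6.2.2 | Listed, outside the scanner |
| Post-rTMS threshold | 6.2.5 | Not listed |
| Post-rTMS threshold | 9.6.1 | 30 / 5 = 6 time points, counted from 5 to 30 minutes |
| Test on temperatures | 9.6.1 | Linear mixed model, 0.05; no terms or time summary |
| Test on ratings | 9.6.1 | ANOVA, 0.05; status not stated |

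**2. Does another section supply the missing model?** Section 9.2 writes out a mixed model with time index 1 and 2, time scores 0 and 1, a random intercept, the arm effect at baseline fixed at zero, and an arm effect on the change. The random slope is fixed at zero because there are only two time points. The temperature series has one pre-rTMS value and six post-rTMS values, so this model does not say how time enters or which arm contrast is the result. Sections 9.2 and 9.7 also treat baseline versus post as one univariate contrast, which needs a single post value. None is chosen for the series.

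**3. Size of the multiplicity, if either test could be read as the clinical result.** The protocol gives no figure to reproduce. Inputs: two two-sided tests at 0.05 (Section 9.6.1) and a correlation r between their statistics, which the documents do not give and which is assumed. With bivariate normal statistics under no effect,

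P(at least one significant) = 1 − P(|Z1| < 1.96 and |Z2| < 1.96).

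- r = 0: 1 − 0.95² = 0.0975
- r = 0.5: 0.0907
- r = 0.9: 0.0704

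**4. The non-hypnosis run.** Sections 6.2.2 and 6.2.5 acquire hypnosis and non-hypnosis pain runs before and after rTMS. The ratings ANOVA in 9.6.1 and the ANOVA for Secondary Outcome E in 9.6.2 contrast baseline with rTMS + HA. Section 9.6.1 lists an assessment after rTMS separately from post-rTMS HA, but for network measures and with no test attached. Its moderate-pain comparison names no run type. On a direct effect of rTMS on pain, Section 9.6.2 calls it possible though unlikely. Section 2.2 argues against one ("suggesting that outside of hypnosis, inhibitory rTMS alone should not exert an independent effect on pain"), but from stimulation over the dACC, whereas this trial stimulates the L-DLPFC.

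**5. Precision of an added HA-minus-non-HA contrast.** If the pre-to-post change has SD s in each run type and correlation ρ between them, the variance of the difference is 2s²(1 − ρ). The standard error relative to the HA-only change is √(2(1 − ρ)): 1.41 at ρ = 0, 1.00 at ρ = 0.5 and 0.71 at ρ = 0.75. The values of ρ are assumed. These figures are for unadjusted change scores, so they only indicate what a baseline-adjusted version would give.

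**The case against.** The strongest reply is that this is an omission in a procedures list. Nothing in Section 6 says that thresholds are not repeated. The fixed stimulus is for the scanner sessions and threshold testing is done outside the scanner, so the two can coexist. Section 6.2.5 is visibly carried over from the pre-rTMS text: the analgesia part heads its scans as pre-TMS and calls the HIP a baseline measure. Section 6 is also incomplete elsewhere, since the HIS is scheduled in 6.1 but not described in 6.2. The pain-induction row may cover threshold testing, and the hypnotic analgesia manual (Appendix 4) is not in the text available. All of this stands. A reader might infer that no post-rTMS threshold was taken; the documents do not support that.

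A reader might also infer that the outcome variable is undefined. It is not: thresholds are named consistently, and the ratings paragraph in 9.6.1 itself opens with pain thresholds as its aim. What is missing is the status of the ratings ANOVA and a summary of the series. Nor is the mixed model wholly unspecified, since 9.2 gives terms, though for two time points only.

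Section 9.2 says that for this hypothesis effect sizes matter more than p-values. That softens the multiplicity point. It does not remove the need to say which variable, at which time, the effect size describes.

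On the non-hypnosis run, it is fair to say that active + HA versus sham + HA is a valid randomised comparison and that the protocol itself discloses the possibility of a direct effect. A reader might call the comparison confounded; it is not. It estimates the effect of adding rTMS to HA, and separating enhancement from a direct effect is a further question.

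**Conclusion.** The mismatch is real and should be fixed. The outcome named in 1.1 and 9.7 cannot be computed from Section 6 as written, and the series that would supply it appears only in 9.6.1, without a model or summary that fits six post-rTMS points. The ratings ANOVA stands beside it with no stated rank. If either test could be taken as the clinical result, the false-positive chance is 7.0% to 9.75% instead of 5%, on the assumed correlations. That figure applies only if the choice is left open.

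The conclusion rests on comparing the sections, not on a claim about what was collected. It concerns the Relevant Clinical Outcome, not the primary connectivity outcome. The SAP does not settle it.

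The non-hypnosis point is secondary. The HA comparison supports a statement about rTMS added to HA but does not by itself show that HA was enhanced. The documents give no size for a direct effect, so none is put on this limit.

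**What to change.** - Reconcile 6.2.2 and 6.2.5 with 9.6.1 and 9.7, stating which pain measures were taken after rTMS and when.
- If post-rTMS thresholds were taken, keep change in pain threshold as the single clinical outcome and list the series in 6.2.5. State one time summary, or one mixed-model arm contrast over the 5-to-30-minute points adjusted for the pre-rTMS threshold. Label the ratings ANOVA supportive.
- If none was taken, redefine the outcome in 1.1 and 9.7 and in the Précis, and say so.
- The SAP says that data were collected, so document the choice before the pain data are analysed, or label it post hoc.

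Optional addition, if ratings were recorded in the non-hypnosis runs: report as supportive the arm effect on the post-rTMS HA-minus-non-HA rating, adjusted for its pre-rTMS value, together with the arm difference in the non-HA run. Keep the HA-only comparison. If those ratings were not recorded, limit the conclusion to the combined rTMS + HA effect.

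The cost is wording in a few sections and one or two extra models. Rewording cannot create thresholds that were not measured. The added contrast loses precision when the two runs are weakly correlated, isolates enhancement only if the direct effect is similar in both run types, and speaks to ratings rather than thresholds.
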